The endpoint for Aim 1 for the intervention arm is the successful completion of the follow-up period, including food and nutrition security status, total fruits and vegetables selected per visit, total energy intake, intake of key food groups, and time to obtain food from food pantry per visit.

The endpoint for Aim 2 is the completion of data analysis.

Study Population

The study population for Aim 1 is a sample of low-income adults aged ≥ 18 years..

Accrual Ceiling

We require a total sample size of 193 participants per condition for Aim 1 (total n=386).

Aim 2 will not involve participant enrollment.

Phase

Not applicable.

Description of Sites/Facilities Enrolling Participants

We propose to recruit participants from food pantry clients at food pantry sites within the Met Council Kosher Food Pantry Network, a network that contains 65 pantry partners and over 200 community partners in NYC. Met Council procures and distributes kosher food to their network of kosher food pantries and provides ongoing support with reporting, pantry set up and maintenance, advocacy, and programming. The Network primarily serves immigrants, seniors living on fixed incomes, the un- and underemployed and anyone else in need in immigrant-dense neighborhoods.

Study Duration

The study will last 18 months, but data collection will specifically occur in 2 time periods, including months 4-6 and 10-12 in Year 1 of the study.

Participant Duration

The total participant duration will be approximately 30-50 minutes to complete the survey and record food selections for both data collection periods.

Schedule of Activities (SoA)

During the baseline data collection period, all participants will complete a survey about their food and nutrition security, diet behaviors, and frequency of food pantry visits. To finish, the Research Assistant will record their food selections from the current food pantry visit.

During the follow-up data collection period, all participants will complete a survey about their food and nutrition security, diet behaviors, and frequency of food pantry visits. Participants in the control arm will record their food selections from their most recent food pantry visit and send them to the study team.

End of Study Definition

The end of the study is when we have disseminated our results.

1 – Statement of Compliance

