3.1 Primary Objective

Our primary objectives are to determine whether the transition to online ordering at a choice-based food pantry network influences food security status among low-income adults and determining whether there are differences in impact by age group.

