5.5 Strategies for Recruitment and Retention

For Aim 1, we will choose the food pantry recruiting sites with help from Met Council Kosher Food Pantry Network. We will aim to select a control site that is similar to the intervention site based on food pantry characteristics (e.g., number of food pantry clients per week, primary language(s) spoken) and community-level characteristics (e.g., neighborhood poverty level).

IRB-approved NYULH study personnel will recruit participants in person at two Met Council food pantries and will obtain permission from the food pantries prior to in-person recruitment at their

facilities. We will have support from food pantry staff members in introducing the NYULH study to potential participants. The study personnel will be on-site at the food pantry to introduce the study to food pantry clients and answer questions. Food pantry staff will also be available to direct food pantry clients to the study personnel. The study team will provide the food pantry with a recruitment flyer to post and/or pass out informing clients of the study and directing them to scan a QR code for the consent form with more information about the study and access to the study team's contact information. After scanning the QR code, clients will first see a short paragraph ("Pre-Consent QR Code Copy") listing the eligibility requirements and explaining what the consent is, in addition to a note that they do not need to sign the form at that moment. After the short paragraph, they will be able to scroll down to view the consent.

We will collect names, phone numbers, email addresses, and mailing addresses from participants in a secure REDCap form to facilitate the follow-up data collection, which will be conducted virtually, and to distribute gift cards.

Screen failures include those who do not meet all of our inclusion criteria. Potential participants will be asked to answer one pre-screening question about their age to determine their eligibility. If they do not meet our inclusion criteria, these participants will be told by the Research Assistant, "Thank you for your time, but unfortunately, you are not eligible for this study." We will immediately discard information from screen failures and from individuals that do not provide consent to take part in this study. Re-screening is not applicable.

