8.2 Sample Size Considerations

To calculate our sample size, we used estimates from a similar study that found that a food bank-delivered intervention (diabetes-appropriate food packages, text-based health education, and referrals to health care) resulted in a decrease in the mean food security score from 2.8 to 2.3, or a 6.3% decrease in the percentage of participants with low or very low food security status.⁴⁰ Based on this study, we assume the standard deviation of the food security score is 1.5 and estimate that 155 participants in each condition (total n=310) will provide 90% power to detect a 0.5 difference in food security score between experimental and control conditions. To account for a potential attrition rate of 20% in the follow-up period, we plan to recruit a total sample size of 193 participants per condition (total n=386).

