8.4.2 Analysis of the Primary Efficacy Endpoint(s)

The primary outcome for Aim 1 is food security status. We will use the United States Department of Agriculture (USDA) six-item food security survey module to assess food security status, where the range of points is zero to six points, and higher points corresponds to lower food security.⁴¹ Food security status will be categorized according to USDA guidelines, including very low (5-6); low (2-4); and high or marginal (0-1) food security. We will perform a linear regression to assess balance of demographic characteristics between conditions; because of the natural experiment design, these characteristics should be balanced. To assess differences in outcomes between study conditions, we will regress the outcome variable on indicator variables for the experimental conditions, with the control condition as the reference group; if necessary, we will also adjust for any respondent characteristics that may be unbalanced by condition.

The primary outcome for Aim 2 is the same as Aim 1 and measured using the same specifications. We will test for potential interaction effects at the individual-level by adding an interaction term for age group (18-61 vs. ≥ 62 years). In the food pantry network, an average of 25% of clients served are above 61 years of age, so we will have adequate variation to assess potential interactions by age group.

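### With one pantry per condition, the primary p-value, interval and 90% power apply to an effect of online ordering only if pantry-level variance is zero, and the plan does not say so

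*Combined protocol and SAP*

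**What the plan says.** The primary objective (3.1) is to "determine whether the transition to online ordering at a choice-based food pantry network influences food security status among low-income adults". Section 4.1 describes one pantry not scheduled to transition (control) and one that is (intervention). Section 5.5 confirms the count: staff will "recruit participants in person at two Met Council food pantries". The Synopsis speaks of sites without giving a number. Under 5.4 the pantry makes the change itself, not the researchers.

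For the sample size, 8.2 states "we assume the standard deviation of the food security score is 1.5" and concludes that "155 participants in each condition (total n=310) will provide 90% power to detect a 0.5 difference in food security score". It gives no significance level and does not say whether the test is one- or two-sided.

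The primary model in 8.4.2, repeated in 8.4 and 8.4.8, is an individual-level linear regression: "we will regress the outcome variable on indicator variables for the experimental conditions, with the control condition as the reference group". Respondent characteristics are added only if they prove unbalanced. The model has no pantry term, no baseline score and no time term. Neither the sample size section nor the analysis sections mention clustering, an ICC, a design effect or pantry-level variance.

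**The concern.** The standard error of the condition coefficient comes from about 310 people treated as independent. That is the right reference for asking whether the clients of these two pantries differ. The objective asks something else, namely whether online ordering changes food security. For that question, two pantries can differ at follow-up, or drift apart between the two survey periods, although online ordering does nothing. Any such difference goes into the coefficient in full and into its standard error not at all.

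If the pantry component is not zero, the p-value is too small, the interval too narrow and the power too high as statements about online ordering. This matters because 2.3.2 expects the food pantry network and other pantries to use the result when deciding whether to transition. The problem is separate from respondent imbalance: it remains even if the two client groups match perfectly on measured characteristics.

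**Working it through.** **Inputs from the documents.** SD 1.5, difference 0.5 and 155 analysed per condition (8.2); one pantry per condition (4.1, 5.5). **Assumed:** ICC values of 0.001 to 0.02, with SD 1.5 applying to the outcome analysed.

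**Step 1: reproduce the plan's figure.**

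- SE = 1.5 × sqrt(2/155) = 0.170, and 0.5/0.170 = 2.93.
- One-sided 5%: power = Φ(2.93 − 1.645) = 90.1%, and the required number is 155 per condition. This matches 8.2.
- Two-sided 5%: power = Φ(2.93 − 1.96) = 83.5%, and 190 per condition would be needed. This does not match.

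So the stated figure follows from person-level variance alone, on a one-sided 5% basis that 8.2 does not state.

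**Step 2: add a pantry component.** With one pantry of m = 155 per condition:

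- design effect DE = 1 + (m − 1) × ICC = 1 + 154 × ICC
- SE allowing for pantry = 0.170 × sqrt(DE)
- actual two-sided error = 2 × [1 − Φ(1.96/sqrt(DE))]
- actual one-sided error = 1 − Φ(1.645/sqrt(DE))
- power = Φ(0.5/SE − 1.645) one-sided, or Φ(0.5/SE − 1.96) two-sided

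| Assumed ICC | DE | SE | Error, two-sided 5% | Error, one-sided 5% | Power, one-sided 5% | Power, two-sided 5% |
|---|---|---|---|---|---|---|
| 0 | 1.00 | 0.170 | 5% | 5% | 90% | 84% |
| 0.001 | 1.15 | 0.183 | 7% | 6% | 86% | 78% |
| 0.005 | 1.77 | 0.227 | 14% | 11% | 71% | 60% |
| 0.01 | 2.54 | 0.272 | 22% | 15% | 58% | 45% |
| 0.02 | 4.08 | 0.344 | 33% | 21% | 42% | 31% |

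The power columns treat the pantry variance as known. Simulating the individual-level t-test with no effect (20,000 runs per ICC) gave two-sided error of 6.5%, 14.0%, 22.5% and 33.5% at the four non-zero ICCs.

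**Step 3: put it in points.** Between-pantry SD = 1.5 × sqrt(ICC). An ICC of 0.01 is therefore a between-pantry SD of 0.15 points on the 0 to 6 scale. The 95% half-width (1.96 × SE) is 0.33 points at ICC 0, 0.44 at 0.005, 0.53 at 0.01 and 0.67 at 0.02.

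**Step 4: can more clients help?** As m grows, SE falls only to 1.5 × sqrt(2 × ICC). Setting this equal to 0.5/(1.645 + 1.282) gives ICC = 0.0065. Above that value, no number of clients at two pantries gives 90% power at one-sided 5%. At two-sided 5% the limit is 0.0053.

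**Step 5: can the trial estimate the ICC?** Two pantries less two condition means leaves 0 degrees of freedom. Neither cluster-robust errors nor a random pantry effect can supply the component.

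**The case against.** The strongest reply is that the documents contain no between-pantry variance, so every error rate above 5% rests on an assumed ICC. That stands. A reader might infer that even slight variation between pantries makes the test reject far too often. The documents do not support that: at ICC 0.001 the two-sided error is about 7%, and the inflation becomes serious only from roughly 0.005 upward. Nor do they report differences in stock, opening hours or local conditions between the two sites.

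Second, 5.5 aims for a control site similar in client numbers, language and neighbourhood poverty, and the Synopsis says food is procured and distributed across the network. Both may make the pantry component small. Neither puts it into the standard error.

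Third, baseline data exist, and 8.1 frames the hypothesis as improvement in one arm and not the other. A change-score or baseline-adjusted analysis would remove or reduce stable pantry differences, and the SD need not then be 1.5. This also stands. The written model has no such term, however, and pantry-specific change over time would still be indistinguishable from online ordering.

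Fourth, with two purposively chosen pantries the same defect could be called site confounding, since the error rates average over hypothetical draws of pantries. That is a fair alternative description, but the plan's interval omits the component under either name. The appeal to random assignment in 4.2, 8.4 and 8.4.8 does not help: no randomisation is described, 5.4 says the pantry makes the change, and randomising two pantries would still leave one unit per arm.

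**Conclusion.** The concern holds in conditional form. Condition and pantry are fully aliased, and the primary p-value, interval and stated power are valid for an effect of online ordering only if pantry-level variance, including differential change over time, is zero. Section 8.2 does not state that condition, and the 90% also needs a one-sided 5% test that it does not state.

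The size depends on an ICC that the documents do not give and the trial cannot estimate. The tabulated range assumes SD 1.5 and 155 analysed per pantry. It runs from mild at ICC 0.001 to serious from about 0.005.

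Two stronger readings should be avoided. One is that the test's true error rate is known to be badly inflated; no document figure shows this. The other is that a causal conclusion must be barred unless the result survives a particular ICC. No value in the documents could set that bar.

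**What to change.** 1. **Section 8.2.** State alpha and sidedness. Say that the power assumes no pantry-level variance, and show it on that one basis over a stated ICC range, for example 0.001 to 0.02.

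2. **Sections 8.4, 8.4.2 and 8.4.8.** Describe the regression p-value and interval as inference about clients of these two pantries. Next to the primary estimate, report intervals with the variance multiplied by 1 + (m − 1) × ICC over the same range, where m is the number analysed per pantry. Also report the ICC at which the result stops being significant. For a two-sided 5% test with observed statistic z, that is [(z/1.96)² − 1]/(m − 1). An estimate of 0.5 with SE 0.170 and m = 155 gives [(2.93/1.96)² − 1]/154, or about 0.008. Label this a sensitivity analysis under assumed ICCs for the outcome actually analysed.

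3. **Interpretation.** State as a limitation that the result is a two-pantry comparison, and that attributing it to online ordering depends on how plausible a pantry component below the tipping-point ICC is.

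The cost is protocol and SAP wording plus a few lines of analysis. The downside is wider reported intervals and a less favourable power statement. No extra participants are needed.

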8.4.3 Analysis of the Secondary Endpoint(s)

The secondary outcomes for Aim 1 include changes in: 1) total cup-equivalents of fruits and vegetables selected per visit; 2) intake of fruits and vegetables; 3) time to obtain food from food pantry per visit (minutes); and 4) individual-level frequency of food pantry visits per month (n). To capture a potential increase in *new* clients visiting the food pantry due to the transition to online ordering, we will also measure changes in the frequency of food pantry visits per month at the food pantry-level (n).

The primary outcome for Aim 2 is the same as Aim 1 and measured using the same specifications, including number of fruits and vegetables selected per visit; total energy intake; intake of key food groups; time to obtain food from food pantry per visit; and individual-level and food pantry-level frequency of food pantry visits per month. For assessing differences in the frequency of food pantry visits per month at the food pantry-level, we will add an interaction term for age group, which the food pantry network measures as child (<18 years), adult (18-61 years), and older adult (≥ 62 years).

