8.1 Statistical Hypotheses

In Aim 1, we will test the working hypotheses that 1) food security will improve (i.e. food security score will decrease) among participants visiting a food pantry that transition to online ordering in the follow-up period, but not among those in the control arm, and 2) participants visiting a food pantry that transitions to online ordering will also select more fruits and vegetables per visit, have higher fruit and vegetable intake, and spend less time accessing food pantries in the follow-up (vs. baseline) period compared to those in the control arm.

For Aim 2, we hypothesize that improvements in food security due to online ordering will be larger for younger adults.

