8.4 Statistical Analyses

We will perform a linear regression to assess balance of demographic characteristics between conditions; because of the natural experiment design, these characteristics should be balanced. To assess differences in outcomes between study conditions, we will regress the outcome variable on indicator variables for the experimental conditions, with the control condition as the reference group; if necessary, we will also adjust for any respondent characteristics that may be unbalanced by condition. The design and methods proposed will achieve robust and unbiased results because random assignment to an intervention group or control group in the context of a natural experiment minimizes bias.

We will also test for potential interaction effects at the individual-level by adding an interaction term for age group (18-61 vs. ≥ 62 years). In the food pantry network, an average of 25% of clients served are above 61 years of age, so we will have adequate variation to assess potential interactions by age group. For assessing differences in the frequency of food pantry visits per month at the food pantry-level, we will also add an interaction term for age group, which the

food pantry network measures as child (<18 years), adult (18-61 years), and older adult (≥ 62 years).

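### Produce selected per visit is analysed as an unscaled total with household size neither recorded nor a named covariate; recording it and adjusting for it is a cheap safeguard.

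*Combined protocol and SAP*

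**What the plan says.** Section 8.4.3 lists changes in "total cup-equivalents of fruits and vegetables selected per visit" as the first secondary outcome for Aim 1. The Aim 2 paragraph of the same section words it as a count, "number of fruits and vegetables selected per visit", also without a denominator. Section 8.1 sets the contrast as a comparison "in the follow-up (vs. baseline) period compared to those in the control arm".

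The model is given in 8.4.2 and repeated in 8.4 and 8.4.8: "we will regress the outcome variable on indicator variables for the experimental conditions, with the control condition as the reference group". It has no term for the baseline value or for time. Covariates are conditional and unlisted: "if necessary, we will also adjust for any respondent characteristics that may be unbalanced by condition".

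Participants come from one control and one intervention pantry (4.1, 5.5). Section 5.5 gives examples of matching factors: weekly client volume, language and neighbourhood poverty. Section 2.3.1 limits survey content to food and nutrition security, key foods and visit frequency. For pantry-level visit counts, 8.4 gives the age groups that the "food pantry network measures as child (<18 years), adult (18-61 years), and older adult (≥ 62 years"), so children are among those counted, although only adults enrol (5.1).

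**The concern.** If an enrolled adult collects food for a household, the total per visit probably depends on how many people it feeds. With one pantry per arm, any difference in family size between the pantries is fully confounded with condition. The conditional adjustment clause helps only if household size is measured and treated as a respondent characteristic, and the text shows neither. At stake is the selection hypothesis in 8.1: part of an apparent gain or loss in produce selected could reflect who uses each pantry and not the ordering system.

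**Working it through.** **The plan's own figures.** The documents give no mean, SD, effect size or household-size distribution for cup-equivalents. The only sample-size figure is 155 analysable per condition (8.2), for the food security score. It reproduces with a one-sided 5% test: 2 × 1.5² × (1.645 + 1.282)² / 0.5² ≈ 154.2, rounded up to 155. Sidedness is not stated and is a separate matter. Here 155 serves only as the number per arm.

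**Assumed inputs (none from the documents).** Total = household size H × cup-equivalents per member c. Mean c = 4 with coefficient of variation (CV) 0.5; H = 1 + Poisson, mean 3 in the smaller-family pantry; two-sided 5% t tests; no true effect unless stated. Let d be the gap in mean household size and t a proportional change over time shared by both arms.

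**Step 1: expected false difference.**
- Follow-up totals alone, no trend: 4 × d.
- Change in totals: 4 × t × d.

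| Gap d | Follow-up only, t = 0 | Change, t = 0 | Change, t = 10% | Change, t = 25% |
|---|---|---|---|---|
| 0.5 | 2 | 0 | 0.2 | 0.5 |
| 1 | 4 | 0 | 0.4 | 1.0 |
| 1.5 | 6 | 0 | 0.6 | 1.5 |
| 2 | 8 | 0 | 0.8 | 2.0 |

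**Step 2: false rejection by simulation, 155 per arm.**
- Change, means 3 and 4.5, within-person correlation 0.4: about 5% with no trend; about 8% with a 10% trend (mean false difference about 0.6).
- Change, correlation 0.5, 25% trend: 8% at a gap of 0.5 and 15% at a gap of 1.
- Follow-up totals alone, correlation 0.5, no trend: about 46% at a gap of 0.5 and 94% at a gap of 1.

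**Step 3: share of single-visit variance due to household size.** Share = CV_H² / [(1 + CV_H²)(1 + CV_c²) − 1].
- CV_H = 0.2, CV_c = 0.8: 0.04 / 0.7056 = 6%.
- CV_H = 0.8, CV_c = 0.3: 0.64 / 0.7876 = 81%.

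The share could therefore be trivial or dominant.

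**Step 4: per-member scaling or a covariate.** How the total depends on household size was varied. Power is for a true 20% effect; null rejection is for means 3 and 4.5 with a 10% trend.

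| Total depends on household size | Power, raw change | Power, per member | Null rejection, raw change | Null rejection, per member |
|---|---|---|---|---|
| In proportion | about 80% | about 88% | about 8% | about 5% |
| As its square root | about 86% | about 86% | – | – |
| Not at all | about 88% | about 77% | about 5% | about 9% |

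In the last row, per-member null rejection ranged from about 8% to 15% over the settings tried. Keeping the total and adding household size as a covariate held null rejection at about 4% to 6% under all three patterns, with no loss of power against the unadjusted change.

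**The case against.** The strongest reply is that 8.4.3 defines the outcome as a change and 8.1 compares follow-up with baseline against control. A stable family-size gap then cancels within each participant. This stands: without a shared trend there is no bias, and with a 10% trend the bias is small beside totals of about 12 to 18 cup-equivalents (4 × 3 and 4 × 4.5). It is not a full answer, because the model in 8.4.2 contains no baseline term and does not exclude a follow-up-only regression.

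Second, the plan checks demographic balance and allows adjustment; the matching factors in 5.5 are examples only; and the survey instrument is not in the public text, so household size may be collected after all. All true. Absence from the public text is not proof of absence from the survey, but an unlisted, conditional covariate cannot be relied on.

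Third, no section says that amounts selected depend on household size. The child, adult and older-adult categories show who is counted, not how much an order contains. This also stands. It is why redefining the outcome per member is not recommended: if allotments are fixed, that change costs power and adds the kind of bias it was meant to remove.

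**Conclusion.** The gap is real and modest. The outcome is an unscaled total, household size does not appear in the public text as an item, matching factor or covariate, and each arm is one pantry. If totals rise with household size, an analysis of change is biased only when both arms share a time trend: about 0.6 cup-equivalents and about 8% false rejection at mean households of 3 and 4.5 with a 10% trend. A follow-up-only analysis would be badly biased. All these sizes rest on assumed inputs.

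A reader might infer that family size drives the variance of this outcome, or that any family-size gap between the pantries would appear as an effect of online ordering. The documents support neither. The variance share runs from 6% to 81% over plausible inputs, and a stable gap cancels in a change without a trend. The primary food security score is not affected.

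**What to change.** Record household size at baseline and at follow-up, from one survey item or the pantry's registration field. In 8.4.3, keep the total as the outcome, state that the model uses the change or adjusts for the baseline total, and include household size as a fixed, pre-specified covariate instead of one added only if imbalance is seen. Report cup-equivalents per household member as a sensitivity analysis only.

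The cost is one survey item or data field, a few lines of SAP text, and some error in reported household size. The item is best added before baseline collection, because household size at that visit is harder to recover later.

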However, mistrust of emergency food resources may be disproportionately higher in immigrant (vs. non-immigrant) communities,²⁷ potentially due to stigma, fear of interaction with government representatives (e.g. NYPD, ICE), and other factors.²⁸ Evidence from qualitative research, for example, suggests that the stigma of waiting in public to be served reduces utilization and satisfaction of food pantries.²⁹ This was corroborated by a recent review study noting how food pantry clients describe reasonable wait times and an “easy process” as a cornerstones of good customer service in food pantry settings.³⁰ Thus, strategies to increase food pantry use may support food security and healthy eating behaviors among low-income adults, especially those designed to mitigating the high opportunity costs of waiting in line and stigma, such as digital ordering.

In the Parent Grant, we are leveraging the rapid growth in online grocery shopping and expansion of retailers accepting SNAP benefits in online transactions. The recent shift to online ordering in some food pantries affords a similar opportunity to support food security and a healthy diet among low-income adults, which we aim to leverage in this Administrative Supplement. Online ordering is available in a small number of food pantries across the U.S., such as the Portland Open Bible Community Pantry in Portland, OR and The Open Door in Essex County, MA, largely due to increases in food insecurity and social distancing measures during the COVID-19 pandemic.^{31,32} Anecdotal evidence suggests online ordering has contributed to increased food pantry use, potentially due to reductions in wait times, reduced stigmatization, and increases in self-efficacy and self-sufficiency.³³⁻³⁷ Increases in food pantry, in

turn, may improve food pantry clients' food security status and increase fruit and vegetable intake relative to a traditional distribution model,^{38,39} especially in combination with changes to food "pricing" (e.g., assigning foods with high nutritional value fewer points than less healthy food). To our knowledge, however, there have been no evaluations of the transition to online ordering in food pantries.

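### The pantry-level outcome in 8.4.3 is meant to capture new clients but is defined by visits, which also rise when existing clients come more often

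*Combined protocol and SAP*

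**What the plan says.** Section 8.4.3 gives the pantry-level outcome one purpose: "To capture a potential increase in *new* clients visiting the food pantry due to the transition to online ordering". The measure that follows is the change in visits: "we will also measure changes in the frequency of food pantry visits per month at the food pantry-level (n". The same paragraph lists, as secondary outcome 4, "individual-level frequency of food pantry visits per month (n", which is measured in enrolled participants.

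The only further detail on the pantry-level outcome, in 8.4, 8.4.3 and 8.4.8, is an interaction with age group, which the "food pantry network measures as child (<18 years), adult (18-61 years), and older adult (≥ 62 years"). No section plans a count of first-time or distinct clients, a split of visits into new and returning clients, or a subtraction of existing clients' visits from the pantry total.

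The Background (2.1) gives the expected direction: "Anecdotal evidence suggests online ordering has contributed to increased food pantry use". It does not limit that increase to people who are new to the pantry.

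**The concern.** The purpose and the measure do not match. A pantry's monthly visits can grow because more people come, because the same people come more often, or both. The reasons offered in 2.1 (shorter waits, less stigma) apply to existing clients as well as to newcomers. A control pantry does not separate the two, because more frequent visits by existing clients at the intervention pantry would themselves be an effect of online ordering.

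Under 4.1 and 6.1, participants enrol before the change, so the survey cohort contains nobody who first came because of it. The pantry-level outcome is therefore the plan's only direct look at reach. If it is read as its purpose clause invites, a change in habits among existing clients could pass for new clients. A real gain in new clients could also be hidden if mean frequency fell. Section 2.3.2 expects pantries to consult the results when deciding whether to adopt online ordering, so the distinction has practical use.

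**Working it through.** The plan states no effect size, variance or sample size for this outcome, so there is no figure to reproduce. The check is an identity applied to assumed values.

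**Inputs**
- Purpose, measure and outcome 4: from 8.4.3.
- Clients per pantry and visits per client: not given. Section 5.5 names "number of food pantry clients per week" as a site-matching characteristic but gives no value. Assumed: 1,000 clients; 1, 2 or 4 visits per client per month; rises in total visits of 10%, 20% or 30%.

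**Identity.** V = C × f, where V is total visits in a month, C is distinct clients in that month and f is mean visits per client.

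**One rise, several explanations.** Start from C = 1,000 and f = 2, so V = 1,000 × 2 = 2,000. A 20% rise gives V = 2,400, which fits each of these:
- no additional clients, frequency up to 2.4: 1,000 × 2.4 = 2,400;
- 200 additional clients, frequency unchanged: 1,200 × 2.0 = 2,400;
- frequency up to 2.2: 2,400 / 2.2 ≈ 1,091, or about 91 additional clients.

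**Range.** Since V1/V0 = (C1/C0) × (f1/f0), the starting frequency cancels. If mean frequency does not fall, rises of 10%, 20% and 30% fit 0–100, 0–200 and 0–300 net additional clients per 1,000, whether the baseline is 1, 2 or 4 visits each.

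**Masking.** With 20% more clients, V is unchanged if f falls by 1 − 1/1.2 = 16.7%.

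**Does outcome 4 close the gap?** Partly. Dividing the pantry total by mean visits per client gives an estimate of C. But outcome 4 describes a recruited sample of baseline clients, and newcomers may come at another rate. Suppose 1,000 existing clients make 2.2 visits each and 200 new clients make 1 each: V = 2,200 + 200 = 2,400. Dividing by 2.2 gives about 91 additional clients, against a true 200. The result is also net: C1 − C0 is arrivals minus departures, so 91 could be 91 arrivals and no departures, or 191 arrivals and 100 departures.

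**Would distinct clients per month do instead?** Not alone. If 1,000 existing clients each come every second month (assumed), about 500 appear in a given month. If all switch to monthly visits, 1,000 appear, with no new client among them.

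**The case against.** The best defence is that the two frequency outcomes belong together. Outcome 4 tracks existing clients, the pantry-level measure adds everyone else, and reading them side by side tells the scenarios apart: in the example, enrolled clients would average 2.4 visits in the first case and 2.0 in the second. That stands in part. A reader might infer that the study cannot address new clients at all. The documents do not support this, since outcome 4 bears on the split. What is missing is any stated way of combining the two, and the combination would be rough and net.

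Three further points also have force:
- The unit of the network's records is not described. Total visits is the natural reading of 8.4.3, but 8.4.2 speaks of clients served ("an average of 25% of clients served are above 61 years of age"), which hints that some client counts exist. It does not show that the records hold first-visit or registration dates.
- New clients appear in no objective (3.1), endpoint (3.2) or hypothesis (8.1). Section 8.1 also makes no prediction about visit frequency, so one cannot say that the trial hypothesises more visits by existing clients; 2.1 offers only anecdotal background. Nor does anything commit the authors to reporting a rise in visits as new clients.
- Recruitment is at two sites ("will recruit participants in person at two Met Council food pantries"). If the pantry-level comparison uses those two, any difference, including one in first-time clients, is mixed with site-specific trends. A better count does not cure that.

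These points limit the consequence. They do not remove the mismatch between a purpose about new clients and a measure of visits.

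**Conclusion.** The concern holds for the outcome as defined: the change in monthly visits does not identify the change in new clients, and no other section supplies the missing step. The conclusion rests on the wording of 8.4.3 and the identity above, not on any assumed volume. The illustrative range (0 to 200 net additional clients per 1,000 for a 20% rise in visits) shows that the quantity is not identified; it does not estimate a likely error, and it assumes that mean frequency does not fall.

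The change should be made, because it is cheap and alters what this outcome can support. The scope is one secondary outcome; the primary food security analysis is unaffected.

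**What to change.** In 8.4.3, define the new-client outcome as the number of first-time clients per month at each pantry, meaning clients with no earlier visit or registration on record, and request this count from pantry or network records for the baseline and follow-up periods. Keep total visits per month as a separate volume measure. Distinct clients per month may be added as a reach measure, with a note that it does not by itself isolate new clients. Carry the same definitions into the age-group analyses in 8.4 and 8.4.8.

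Before committing, ask the network whether its records identify first-time clients. If they do not, delete the new-client purpose and report the outcome as total visit volume, read alongside outcome 4.

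The cost is a slightly larger data request to the network. The fallback changes wording only and needs no new data.
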